6.14.4. Vital Signs and Other Physical Findings

For the treatment-emergent categorical analyses (shift and treatment emergent), the analysis period is defined as the treatment period plus 30 days off-drug follow-up time. The analysis period for the continuous analyses (e.g., change from baseline) is defined as the treatment period excluding off-drug follow-up time.

Vital signs and physical characteristics include systolic blood pressure (SBP), diastolic blood pressure (DBP), pulse, weight, and BMI. Original-scale data will be analyzed. When these parameters are analyzed as continuous numerical variables, unplanned measurements will be excluded. When these parameters are analyzed as categorical outcomes and/or treatment-emergent abnormalities, planned and unplanned measurements will be included.

The planned analyses described for the laboratory analytes in Section 6.14.3 will be used to analyze the vital signs and physical characteristics.

Table JAHL.6.8 defines the low and high baseline values as well as the criteria used to define treatment-emergence based on post-baseline values. The blood pressure and pulse rate criteria are consistent with the document *Selected Reference Limits for Pulse/Heart Rate, Arterial Blood Pressure (Including Orthostasis), and Electrocardiogram Numerical Parameters for Use in Analyses of Phase 2-4 Clinical Trials Version 1.3* approved on April 29, 2015 as recommended by the Lilly Cardiovascular Safety Advisory Committee (CVSAC).

Table JAHL.6.8. Categorical Criteria for Abnormal Treatment-Emergent Blood Pressure and Pulse Measurement, and Categorical Criteria for Weight Changes for Adults

Parameter (Units of Measure)	Low	High
Systolic Blood Pressure (mm Hg)	≤ 90 (low limit) and decrease from lowest value during baseline ≥ 20 if > 90 at each baseline visit	≥ 140 (high limit) and increase from highest value during baseline ≥ 20 if < 140 at each baseline visit
Diastolic Blood Pressure (mm Hg)	≤ 50 (low limit) and decrease from lowest value during baseline ≥ 10 if > 50 at each baseline visit	≥ 90 (high limit) and increase from highest value during baseline ≥ 10 if < 90 at each baseline visit
Pulse (beats per minute)	< 50 (low limit) and decrease from lowest value during baseline ≥ 15 if ≥ 50 at each baseline visit	> 100 (high limit) and increase from highest value during baseline ≥ 15 if ≤ 100 at each baseline visit
Weight (kilograms)	(Loss) decrease $\geq 7\%$ from lowest value during baseline	(Gain) increase $\geq 7\%$ from highest value during baseline

6.14.5. Special Safety Topics, including Adverse Events of Special Interest

In addition to general safety parameters, safety information on specific topics of special interest will also be presented. Additional special safety topics may be added as warranted. The topics outlined in this section include the protocol-specified AESI.

In general, for topics regarding safety in special groups and circumstances, patient profiles and/or patient listings, where applicable, will be provided when needed to allow medical review of the time course of cases/events, related parameters, patient demographics, study drug treatment and meaningful concomitant medication use. In addition to the safety topics for which provision or review of patient data is specified, these will be provided when summary data are insufficient to permit adequate understanding of the safety topic.

6.14.5.1. Abnormal Hepatic Tests

Analyses for abnormal hepatic tests will involve 4 laboratory analytes: ALT, AST, total bilirubin, and ALP. In addition to the analyses described in Section 6.14.3, this section describes specific analyses for this topic.

First, the number and percentage of patients with the following abnormal elevations in hepatic laboratory tests at any time will be summarized between treatment groups:

- The percentages of patients with an ALT measurement $\geq 3\times$, $5\times$, and $10\times$ the central laboratory ULN during the treatment period will be summarized for all patients with a postbaseline value and for subsets based on various levels of baseline.
 - The analysis of $3\times$ ULN will contain 4 subsets: patients whose non-missing maximum baseline value is $\leq 1\times$ ULN, patients whose maximum baseline is $>1\times$ ULN but $<3\times$ ULN, patients whose maximum baseline value is $\geq 3\times$ ULN, and patients whose baseline values are missing.
 - The analysis of $5\times$ ULN will contain 5 subsets: patients whose non-missing maximum baseline value is $\leq 1\times$ ULN, patients whose maximum baseline is $>1\times$ ULN but $<3\times$ ULN, patients whose maximum baseline is $\geq 3\times$ ULN but $<5\times$ ULN, patients whose maximum baseline value is $\geq 5\times$ ULN, and patients whose baseline values are missing.
 - The analysis of $10\times$ ULN will contain 6 subsets: patients whose non-missing maximum baseline value is $\leq 1\times$ ULN, patients whose maximum baseline is $>1\times$ ULN but $<3\times$ ULN, patients whose maximum baseline is $\geq 3\times$ ULN but $<5\times$ ULN, patients whose maximum baseline is $\geq 5\times$ ULN but $<10\times$ ULN, patients whose maximum baseline value is $\geq 10\times$ ULN, and patients whose baseline values are missing.
- The percentages of patients with an AST measurement $\geq 3\times$, $5\times$, and $10\times$ the central laboratory ULN during the treatment period will be summarized for all patients with a postbaseline value and for subsets based on various levels of baseline. Analyses will be constructed as described above for ALT.

- The percentages of patients with a total bilirubin measurement $\geq 2 \times$ the central laboratory ULN during the treatment period will be summarized for all patients with a postbaseline value and subset into 4 subsets: patients whose non-missing maximum baseline value is $\leq 1 \times$ ULN, patients whose maximum baseline is $> 1 \times$ ULN but $< 2 \times$ ULN, patients whose maximum baseline value is $\geq 2 \times$ ULN, and patients whose baseline values are missing.
- The percentages of patients with an ALP measurement $\geq 1.5 \times$ the central laboratory ULN during the treatment period will be summarized for all patients with a postbaseline value and subset into 4 subsets: patients whose non-missing maximum baseline value is $\leq 1 \times$ ULN, patients whose maximum baseline is $> 1 \times$ ULN but $< 1.5 \times$ ULN, patients whose maximum baseline value is $\geq 1.5 \times$ ULN, and patients whose baseline values are missing.

Information collected from additional hepatic safety data collection forms will be provided in patient profiles.

Second, to further evaluate potential hepatotoxicity, an Evaluation of Drug-Induced Serious Hepatotoxicity (eDISH) plot will be created for all patients whether treated with baricitinib and/or other treatment using the whole study period(s). Each patient with at least 1 postbaseline ALT and total bilirubin will be included in the eDISH; therefore, a patient could contribute 1 or more points to the plot. The points correspond to maximum total bilirubin and maximum ALT, even if not obtained from the same blood draw. Scheduled and unscheduled measures will be used. Another eDISH plot will be provided where maximum AST is used in place of maximum ALT. A listing of patients potentially meeting Hy's rule will be provided (defined as $\geq 3 \times$ ULN for ALT or AST, and $\geq 2 \times$ ULN for total bilirubin, not necessarily at the same time).

When criteria are met for hepatic evaluation and completion of the hepatic safety CRF, investigators are required to answer a list of questions (see Compound level safety standards). A listing of the collected information will be generated together with a graphical patient profile. This includes demographics, disposition, and a display of study drug exposure, AEs, medications, and the liver-related measurements over time will be provided for these patients and any additional patients meeting ALT or AST measurement greater than or equal to $5 \times$ ULN (on a single measurement) or ALP measurement greater than or equal to $2 \times$ ULN (on a single measurement).

6.14.5.2. Hematologic Changes

Hematologic changes will be defined based on clinical laboratory assessments. Common Terminology Criteria for Adverse Events will be applied for selected laboratory tests and are described in the compound level safety standards. These CTCAE grading schemes are consistent with both Version 3.0 and Version 4.03 of the CTCAE guidelines (CTCAE 2003, 2010).

Treatment-emergent laboratory abnormalities occurring at any time during the treatment period and shift tables of baseline to maximum grade during the treatment period will be tabulated. Planned and unplanned measurements will be included. Treatment-emergence will be characterized using the following 5 criteria (as appropriate to the grading scheme):

- any increase in postbaseline CTCAE grade from worst baseline grade

- increase to Grade 1 or above at worst postbaseline
- increase to Grade 2 or above at worst postbaseline
- increase to Grade 3 or above at worst postbaseline
- increase to Grade 4 at worst postbaseline.

Shift tables will show the number and percentage of patients based on baseline to maximum during the treatment period, with baseline depicted by the most extreme grade during the baseline period. With each shift table, a shift table summary displaying the number and percentage of patients with maximum postbaseline results will be presented by treatment group for each treatment period within the following categories:

- Decreased: postbaseline category < baseline category,
- Increased: postbaseline category > baseline category,
- Same: postbaseline category = baseline category.

A laboratory-based treatment-emergent outcome related to increased platelet count will be summarized in similar fashion. Treatment-emergent thrombocytosis as a laboratory-based abnormality will be defined as an increase in platelet count from a maximum baseline value ≤ 600 billion/L to any postbaseline value > 600 billion/L (Lengfelder et al. 1998). Planned and unplanned measurements will be included.

A listing of patients with treatment-emergent thrombocytosis may be provided for safety review.

6.14.5.3. Lipids Effects

Lipids effects will be assessed through analysis of elevated total cholesterol, elevated LDL cholesterol, decreased HDL cholesterol, and elevated triglycerides as described in Section 6.14.3 and with TEAEs potentially related to hyperlipidemia.

Categorical analyses will be performed using National Cholesterol Education Program (NCEP) Adult Treatment Panel (ATP) III guidelines (2002) as shown in the compound level safety standards. The grade-like categories shown in this table are ordered from traditionally most desirable to least desirable for the purposes of these analyses.

Shift tables will show the number and percentage of patients based on baseline to the least desirable category during the treatment period, with baseline depicted by the least desirable category during the baseline period. With each shift table, a shift table summary displaying the number and percentage of patients with the least desirable postbaseline results will be presented by treatment group for each treatment period within the following categories:

- Decreased: postbaseline category more desirable than baseline category,
- Increased: postbaseline category less desirable than baseline category,
- Same: postbaseline category = baseline category.

Treatment-emergent laboratory abnormalities related to elevated total cholesterol, elevated triglycerides, elevated LDL cholesterol, and decreased and increased HDL cholesterol occurring at any time during the treatment period will be tabulated using the NCEP categories shown in the compound level safety standards.

Treatment-emergent elevated total cholesterol will be characterized as follows:

- increase to categories ‘Borderline high’ or ‘High’
- increase to category ‘High.’

Treatment-emergent elevated triglycerides will be characterized as

- increase to categories ‘Borderline high,’ ‘High,’ or ‘Very high’
- increase to categories ‘High’ or ‘Very high’
- increase to category ‘Very high.’

Treatment-emergent elevated LDL cholesterol will be characterized as

- increase to categories ‘Borderline high,’ ‘High,’ or ‘Very high’
- increase to categories ‘High’ or ‘Very high’
- increase to ‘Very high.’

Treatment-emergent abnormal HDL cholesterol will be characterized as

- decreased
 - decrease to categories ‘Normal’ or ‘Low’
 - decrease to category ‘Low’
- increased
 - increase to categories ‘Normal’ or ‘High’
 - increase to category ‘High’.

The percentages of patients with treatment-emergent potential hyperlipidemia will be summarize by treatment, ordered by decreasing frequency in the baricitinib 4-mg group using a predefined MedDRA list of PTs that is a subset of the narrow scope PTs in the MedDRA SMQ ‘Dyslipidemia’ (code 200000026) [see Compound level safety standards].

6.14.5.4. Renal Function Effects

Effects on renal function will be assessed through analysis of elevated creatinine.

Common Terminology Criteria for Adverse Events will be applied for laboratory tests related to renal effects as shown in the compound level safety standards. This CTCAE grading scheme is consistent with both Version 3.0 and Version 4.03 of the CTCAE guidelines. Shift tables will show the number and percentage of patients based on baseline to maximum during the treatment period, with baseline depicted by highest grade during the baseline period. Treatment-emergent laboratory abnormalities related to elevated creatinine occurring at any time during the treatment period will be tabulated. Refer to the Compound level safety standards for details.

6.14.5.5. Elevations in Creatine Phosphokinase (CPK)

Elevations in creatine phosphokinase (CPK) will be addressed using CTCAE criteria as shown in the compound level safety standards. This CTCAE grading scheme is consistent with both Version 3.0 and Version 4.03 of the CTCAE guidelines. Analyses will be the same as the CTCAE analyses specified for laboratory tests related to renal function events in Section [6.14.5.2](#).

A listing of elevated CPK (CTCAE grade of 3 or above) will be provided for medical safety review.

Treatment-emergent adverse events potentially related to muscle symptoms may be analyzed, based on reported AEs. The Muscle Symptoms special search category is a pre-defined MedDRA search criteria list that contains the narrow scope terms from the Rhabdomyolysis / myopathy SMQ (code 20000002) plus selected terms from the Musculoskeletal SOC. These terms are shown in the compound level safety standards.

6.14.5.6. Infections

Infections will be defined using all the PTs from the Infections and Infestations SOC as defined in MedDRA. Serious infection will be defined as all the infections that meet the SAE criteria.

The number and percentage of patients with TEAEs of infections, serious infections, and infections resulting in permanent study drug discontinuation will be summarized by treatment group using MedDRA PTs. The proportion of patients developing skin infections requiring antibiotic treatment by Week 16 will also be summarized on the overview of infections table.

The number and percentage of patients with TEAEs of infections by maximum severity will be summarized by treatment group using MedDRA PTs.

Treatment-emergent infections will be reviewed in context of other clinical and laboratory parameters via a listing (details see Compound level safety standards).

The TEAE infections will be further analyzed in terms of potential opportunistic infection, herpes zoster and herpes simplex. Summary of HBV DNA monitoring results and association between infection and neutropenia/lymphopenia will also be provided in the context of infections.

Opportunistic infection

To identify potential opportunistic infections (POIs), the following approach will be used:

- identifying the POIs using a list of MedDRA PTs (refer to the compound level safety standards).

POIs identified through these search approaches may be combined in one list for medical assessment and final classification of whether the case met the modified Winthrop definitions for OI.

A final listing for OIs will be provided for the CSR and to assist the composition of patient narratives.

Herpes zoster

Cases of herpes zoster will be further classified as follows:

- localized or non-multidermatomal-involvement of the primary and/or adjacent dermatomes only

- complicated – documented ocular (cornea or deeper structure; for example, iritis, keratitis, retinitis, etc.) or motor nerve involvement (e.g., palsy; post herpetic neuralgia [PHN] does not meet criteria for motor nerve involvement).
- uncomplicated-localized or non-multidermatomal cases that are not complicated
- multidermatomal-involvement beyond primary and adjacent dermatomes (that is, >3 contiguous dermatomes) or involvement of two or more non-contiguous dermatomes
 - complicated-documented ocular (cornea or deeper structure; for example iritis, keratitis, retinitis, etc.) or motor nerve involvement
 - uncomplicated-multidermatomal cases that are not complicated
- disseminated-systemic infection, widespread, often bilateral with or without internal organ involvement (i.e., visceral involvement) and other systemic signs/symptoms.
- Recurrent - >1 infection occurring in an individual patient during the course of participation in the baricitinib clinical program.

All herpes zoster will undergo medical review to determine the classification as described above.

A summary of herpes zoster table will be provided. The summary table will also include event maximum severity, seriousness, whether resulting in temporary study drug interruption, whether resulting in study drug discontinuation, whether treated with antiviral medication, and event outcome. The incidence rate adjusted for observation time will also be provided (as defined in Section 6.14.2). Of note, in the context of herpes zoster, antiviral medication treatment is defined as that the medication was initiated at the event start date, or within 30 days before or after the event start date. The antiviral medication for herpes zoster includes but not limited to Aciclovir, Brivudine, Cidofovir, Famciclovir, Foscarnet, Ganciclovir, Penciclovir, Valaciclovir, Valganciclovir, Vidarabine (best presented by J05AB, J05AC, J05AE, and J05AH ATC codes). For specific data lock, medical representatives will review the concomitant medication list and make adjustment of the above list if necessary.

If a patient has more than 1 event of herpes zoster, the event with the maximum severity will be used in these summary tables. If more than 1 event of herpes zoster occurs with the same severity, the event with the longest duration will be used in the summary table.

Herpes simplex

A summary analysis of herpes simplex will be provided. Herpes simplex will be defined based on MedDRA PT as listed in the compound level safety standards (both narrow and broad terms in the herpes simplex section). The list needs to be reviewed by GPS/medical prior to data locks (final and interim). The summary table will also include event maximum severity, seriousness, whether resulting in temporary study drug interruption, whether resulting in study drug discontinuation, and whether treated with antiviral medication. The exposure-adjusted incidence rate (EAIR) will also be provided.

If a patient has more than 1 event of herpes simplex, the event with the maximum severity will be used in these summary tables. If more than 1 event of herpes simplex occurs with the same severity, the event with the longest duration will be used in the summary table.

Skin Infections

A summary analysis of skin infections will be provided. Skin infections will be defined based on MedDRA preferred term as listed in Compound level safety standards.

HBV DNA

A listing of patients with detectable hepatitis B virus (HBV) deoxyribonucleic acid (DNA) post baseline will be provided.

HBV DNA status post baseline (not detectable, detectable but not quantifiable [i.e., LLOD], quantifiable [i.e., LLOD]) will be summarized by treatment group stratified by baseline HBV serology status, specifically:

- HBsAb+ / HBcAb+
- HBsAb- / HBcAb+

Association between infection and neutropenia/lymphopenia

To evaluate the association between infection and neutropenia, for the controlled analysis sets, the frequency of infections will be provided by patient subgroups defined by the worst CTCAE grades of neutropenia during the analysis period, respectively. Infection outcomes considered for this analysis are any treatment-emergent infection, serious infection and herpes zoster. For this analysis, no statistical comparison will be provided.

In addition, and depending on the number of cases with CTCAE Grade 2 or greater, a summary table will be provided for treatment-emergent infections that were preceded or accompanied by neutropenia. For this analysis, neutropenia is defined as (1) CTCAE Grade 2 or greater, (2) Grade 3 or greater. Infection events with onset date \leq 14 days before or after the Grade 2 neutrophil count collection date will be considered as infections preceded or accompanied by neutropenia.

Similar analyses as above will be conducted to evaluate the association between infection and lymphopenia.

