6.14.2. Adverse Events

Adverse events are recorded in the eCRFs. Each AE will be coded to system organ class (SOC) and preferred term (PT) using the Medical Dictionary for Regulatory Activities (MedDRA) version that is current at the time of database lock. Severity of AEs is recorded as mild, moderate, or severe.

A TEAE is defined as an event that either first occurred or worsened in severity after the first dose of study treatment and on or prior to the last visit date during the analysis period. The analysis period is defined as the treatment period plus 30 days off-drug follow-up time.

Adverse events are classified based upon the MedDRA PT. The MedDRA Lowest Level Term (LLT) will be used in defining which events are treatment-emergent. The maximum severity for each LLT during the baseline period up to first dose of the study medication will be used as baseline. If an event with missing severity is preexisting during the baseline period, and persists during the treatment period, then the baseline severity will be considered mild for determining treatment-emergence (that is, the event is treatment-emergent if the severity is moderate or severe postbaseline and not treatment-emergent if the severity is mild postbaseline). If an event occurring postbaseline has a missing severity, then the event is considered treatment-emergent unless the baseline is severe, in which case the event is not treatment-emergent. The day and time for events where onset is on the day of the first dose of study treatment will both be used to distinguish between pretreatment and posttreatment to derive treatment-emergence. Should there be insufficient data for AE start date to make this comparison (for example, the AE start year is the same as the treatment start year, but the AE start month and day are missing), the AE will be considered treatment-emergent.

In general, summaries will include the number of patients in the safety population (N), frequency of patients experiencing the event (n), and relative frequency (that is, percentage; $n/N*100$). For any events that are gender-specific based on the displayed PT, the denominator used to compute the percentage will only include patients from the appropriate gender.

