For events of special interest, a more robust incidence rate, IR per 100 patient-years of observation (PYO) may be provided. Patient-years of observation will be calculated as the sum of all patient observation time in the treatment group. For a patient with an event, the observation time will be censored at the event date; for a patient without the event, the observation time will be counted until the end of the analysis period.

PYO will be calculated as follows:

$$PYO = \sum_{pt \text{ w/ event}} \frac{\text{event start date} - \text{first trt dose date} + 1}{365.25} + \sum_{pt \text{ w/o event}} \frac{\text{last observation date} - \text{first trt dose date} + 1}{365.25}$$

IR will be calculated as follows:

$$IR = \frac{\text{number of patients with event}}{PYO} \times 100$$

For each IR provided, a Poisson Distribution 95% CI will be calculated. Treatment group comparisons will be provided based on the incidence rate difference (IRD) together with its 95% CI.

In an overview table, the number and percentage of patients in the safety population who experienced death, an SAE, any TEAE, discontinuation from the study due to an AE, permanent discontinuation from study drug due to an AE, or a severe TEAE will be summarized by treatment group.

The number and percentage of patients with TEAEs will be summarized by treatment group in 2 formats:

- by MedDRA PT nested within SOC with decreasing frequency in SOC, and events ordered within each SOC by decreasing frequency in the baricitinib 4-mg group;
- by MedDRA PT with events ordered by decreasing frequency in the baricitinib 4-mg group.

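### The herpes zoster and herpes simplex tables describe each patient by the most severe event only, so their rows for seriousness, action taken and antiviral treatment can undercount patients

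*SAP*

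**What the plan says.** SAP 6.14.5.6 (Infections) plans a summary table for herpes zoster and another for herpes simplex. For zoster the selection rule is: "If a patient has more than 1 event of herpes zoster, the event with the maximum severity will be used in these summary tables". The tie-break is: "If more than 1 event of herpes zoster occurs with the same severity, the event with the longest duration will be used in the summary". The simplex text repeats both rules, beginning: "If a patient has more than 1 event of herpes simplex, the event with the maximum severity will be used in these summary tables".

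On content, the zoster table covers maximum severity and seriousness, and then "whether resulting in temporary study drug interruption, whether resulting in study drug discontinuation, whether treated with antiviral medication, and event outcome". The simplex table has the same rows apart from outcome. Before the zoster table, the SAP sets out classes to be assigned by medical review: localized, multidermatomal (each complicated or uncomplicated), disseminated ("disseminated-systemic infection, widespread, often bilateral with or without internal organ involvement") and recurrent.

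The severity scale is given in SAP 6.14.2: "Severity of AEs is recorded as mild, moderate, or severe". Seriousness is defined separately, by the outcome criteria in SAP 6.14.2.2, which 6.14.5.6 applies to infections.

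**The concern.** The rule selects an event on one attribute and then reports other attributes from it. Severity grade does not determine whether an event was serious, interrupted or stopped study drug, or was treated with an antiviral. Take a patient with a severe, non-serious zoster episode and later a moderate one that met the SAE criteria and ended treatment. The zoster table shows this patient as non-serious and not discontinued.

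Herpes zoster is named among the adverse events of special interest in Protocol 9.2.2, and readers will go to this table for the character of the zoster cases by arm. If the table drops serious or drug-stopping cases by rule, it understates them and may contradict the serious-infection and discontinuation counts elsewhere in the same report. Elsewhere the SAP takes the worst value over all of a patient's data, for example the worst CTCAE grade (6.14.5.2) and the least desirable lipid category (6.14.5.3).

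**Working it through.** The plan states no figure for this rule, so there is nothing to reproduce. The check applies the rule as written and then compares it with the other planned outputs.

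**1. Applying the rule to a patient with two events.** Let event A carry the attribute (serious, say) and event B not carry it. Each can be mild, moderate or severe, and either can last longer: 3 × 3 × 2 = 18 configurations.

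- A graded higher than B: 3 grade pairs × 2 duration orders = 6. A is kept in all 6, including the 3 in which B lasted longer.
- Equal grades: 3 pairs × 2 orders = 6. A is kept in 3 and lost in the 3 where B lasted longer.
- A graded lower than B: 3 pairs × 2 orders = 6. A is lost in all 6.

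A is kept in 6 + 3 = 9 and lost in 3 + 6 = 9. If a patient is counted whenever any event carries the attribute, A is kept in 18 of 18. These are counts of possible configurations, not probabilities. They show that the loss can arise by grade or by tie-break, and that longer duration alone never displaces a more severe event.

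**2. Direction.** If the selected event carries the attribute, then at least one of the patient's events does. The reverse fails. The one-event count is therefore never above the any-event count.

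**3. Size per affected patient.** Planned arm sizes are in SAP 5.1; the safety population may be slightly smaller.

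- Baricitinib arm: 100 / 120 = 0.83 percentage points.
- Placebo arm: 100 / 240 = 0.42 percentage points.
- Two affected patients: 1.67 or 0.83 points. Three: 2.50 or 1.25 points.

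**4. Where else each attribute is reported.**

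| Attribute | Other planned output |
|---|---|
| Serious | SAE summaries by preferred term and SAE listing (6.14.2.2); serious infections by preferred term (6.14.5.6) |
| Permanent discontinuation | Summary by preferred term and listing (6.14.2.3); infections leading to discontinuation (6.14.5.6) |
| Temporary interruption | Summary by preferred term and listing (6.14.2.3) |
| Antiviral treatment of the herpes event | No other named summary |
| Zoster extent class | No other named summary |

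No one-event rule is stated for the outputs in the first three rows. The same patient can therefore count as serious there and as non-serious in the herpes table.

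**5. Whether extent falls under the rule.** The classification list comes first, and the table content then begins: "The summary table will also include event maximum severity, seriousness, whether resulting in temporary study drug interruption, whether resulting in study drug discontinuation". That wording suggests the classes are in the same table, but the SAP does not say so outright. The recurrent class, meaning more than one infection in a patient, cannot be read from a single event, so at least that row must be derived differently.

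**The case against.** The case against is substantial on reach. The rule is prespecified, is identical in every arm, and keeps every row tied to one real episode. The number of patients with any zoster or simplex event is unaffected. Serious, discontinuing and interrupting events appear in the other outputs tabulated above, and SAP 6.14 says that listings include all safety data. All zoster cases go to medical review. All of this stands, and it limits the point to two descriptive tables.

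The frequency may be low. A patient needs two zoster or two simplex events within 16 weeks of treatment plus 30 days. Protocol 6.2 excludes zoster within 12 weeks before screening, any history of disseminated or complicated zoster, and symptomatic simplex at randomization. Two rows are less exposed than the others. Protocol Table JAHL.4 lists symptomatic zoster, without a grade threshold, as a reason to hold study drug, so both zoster episodes would usually carry an interruption. Antiviral use is credited within 30 days either side of onset, so one course can count for two close episodes. These points stand too.

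Three stronger readings are tempting, and the documents do not support them.

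- A reader might infer that the trial's safety results as a whole undercount serious or drug-stopping herpes events. The other summaries and listings contradict that.
- A reader might infer that time at risk is overstated because the selected event may not be the first. SAP 6.14.2 says "For a patient with an event, the observation time will be censored at the event date" without linking that date to the selected event. For simplex, 6.14.5.6 names an exposure-adjusted rate instead. The inference is not established.
- A reader might attach a percentage loss to the rule. That needs severity mixes, episode durations and a recurrence rate, and the documents give none of them.

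**Conclusion.** The point holds within narrow limits. In the two herpes tables, a patient with more than one event is described by the most severe one, so the rows for seriousness, interruption, discontinuation and antiviral treatment can undercount patients and can conflict with SAP 6.14.2.2, 6.14.2.3 and the infection summaries. The same applies to zoster extent if it is tabulated under this rule, which the wording suggests but does not settle. Disseminated is a class for zoster only, so that part does not extend to simplex.

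Each affected patient costs a row about 0.8 points in a 120-patient arm or 0.4 in the placebo arm, assuming the safety population is close to the planned arm sizes. The number of affected patients cannot be computed from the documents and may be zero. The rule is still worth changing: the events are few, the bias runs one way, and for antiviral treatment and zoster extent no other named summary would reveal the loss. The SAP also provides for patients with more than one event of either infection.

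**What to change.** Replace the paragraph on multiple events, for both infections, with a rule by row:

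- Severity: the maximum over the patient's events. Zoster outcome stays with that event, and the longest-duration tie-break is kept for this purpose.
- Serious, interrupted, discontinued, treated with an antiviral: counted if any of the patient's events has the characteristic.
- Zoster extent: the most extensive class over the patient's events (disseminated, then multidermatomal, then localized), with complicated shown if any event was complicated. State that the class is part of this table.

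As an optional clarification, say that the incidence rate uses the first event.

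The change needs no new data, only SAP wording and modest programming. The cost is that rows of one table may describe different events of the same patient; a footnote should say so.
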